## 5 Statistical Methods and Determination of Sample Size

The statistical analyses will be performed under the responsibility of the Sponsor's Biostatistics platform using SAS® Version 9.4 software or later.

The results of the statistical analysis will be available in the final clinical study report (CSR).

For descriptive purposes, the following statistics will be presented:

**Table 5.1: Descriptive statistics produced**

Baseline characteristics and follow-up description	Categorical data	Number of subjects. Percentage of subjects.
	Continuous data	Mean, standard deviation, quartiles, minimum, and maximum.
Clinical safety results	Categorical data	Solicited: Number and percentage (95% confidence interval [CI]) of subjects and number of events Unsolicited: Number and percentage (95% CIs) of subjects and number of events. Hospitalized suspected dengue case: Number and percentage (95% CIs) of subjects
Immunogenicity results	Categorical data (cutoff)	Number and percentage (95% CIs) of subjects.
	Continuous data (titer / titer ratio)	$\text{Log}_{10}$ : Mean and standard deviation. $\text{Anti-Log}_{10}$ (work on $\text{Log}_{10}$ distribution, and anti- $\text{Log}_{10}$ applied): Geometric mean, 95% CI of the geometric mean, quartiles, minimum, and maximum. Graphical representation by Reverse Cumulative Distribution Curve (RCDC).

The CI for the single proportion will be calculated using the exact binomial method (Clopper-Pearson method, quoted by Newcombe (1), i.e., using the inverse of the beta integral with SAS®).

For immunogenicity, assuming that  $\text{Log}_{10}$  transformation of the titers follows a normal distribution, at first, the mean and the 95% CI will be calculated on  $\text{Log}_{10}$  titers using the usual calculation for normal distribution (using Student's t distribution with n-1 degree of freedom), then antilog transformations will be applied to the results of calculations, in order to provide geometric means (GMs) and their 95% CI.

GM is defined as follows:

$$GM = \left( \prod_{i=1}^n y_i \right)^{1/n} = 10^{\left( \frac{1}{n} \sum_{i=1}^n \log_{10}(y_i) \right)}$$

where  $(y_1, y_2, \dots, y_n)$  are the observed titers or other data where applicable for each subject.

## 5.1 Statistical Methods

In a general way, non-inferiority testing will be performed on dengue immune subjects. The tests will be done only if the number of evaluable subjects provides a global power of at least 80% for the co-primary objectives and secondary objective. In case the global power is insufficient to perform non-inferiority testing, only descriptive analyses will be performed.

Only descriptive analyses will be conducted in dengue non-immune subjects and in the overall population.

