### 5.1.1 Hypotheses and Statistical Methods for Primary Objectives

#### 5.1.1.1 Hypotheses

##### ***Non-inferiority on Cervarix***

The objective is to demonstrate that the humoral immune response to Cervarix administered concomitantly with CYD dengue vaccine is non-inferior to the immune response to Cervarix administered sequentially with CYD dengue vaccine.

Individual hypotheses on Cervarix response for each antigen:

A non-inferiority testing approach will be used to compare geometric mean of titer (GMTs) for the 2 antigens (HPV-16 and HPV-18) 28 days after the last dose of Cervarix, based on the following individual hypotheses:

$$H_0^i: \text{GMT}_{\text{Group1}}^i / \text{GMT}_{\text{Group2}}^i \leq \frac{1}{\delta} \Leftrightarrow \log_{10}(\text{GMT}_{\text{Group1}}^i) - \log_{10}(\text{GMT}_{\text{Group2}}^i) \leq -\log_{10}(\delta)$$

$$H_1^i: \frac{1}{\delta} < \text{GMT}_{\text{Group1}}^i / \text{GMT}_{\text{Group2}}^i > \frac{1}{\delta} \Leftrightarrow \log_{10}(\text{GMT}_{\text{Group1}}^i) - \log_{10}(\text{GMT}_{\text{Group2}}^i) > -\log_{10}(\delta)$$

with:

i, antigen (HPV-16 and HPV-18)

$\delta$  non-inferiority limit is set at 2, ie, 0.301 ( $=\log_{10}[2]$ ), for each antigen "i"

Non-inferiority for antigen i will be demonstrated if the lower bound of the 2-sided 95% CI is greater than  $-\delta$  ( $\alpha=2.5\%$  one-sided).

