#### **5.1.1.2 Statistical Methods**

The non-inferiority test will be performed using the 95% 2-sided CI of the difference of the means of the  $\log_{10}$  transformed post- vaccination titers between Group 1 and Group 2 ( $\alpha=2.5\%$  one-sided). The CI for differences will be calculated using normal approximation of log-transformed titers.

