#### **5.1.2 Hypotheses and Statistical Methods for Secondary Objectives**

##### **5.1.2.1 Hypotheses**

###### ***Non-inferiority on Cervarix***

The objective is to demonstrate that the humoral immune response (in terms of seroconversion) to Cervarix after concomitant administration with CYD dengue vaccine is non-inferior to sequential administration with CYD dengue vaccine measured 28 days after the last dose of Cervarix.

A non-inferiority testing approach will be used to compare seroconversion rates for the 2 antigens (HPV-16 and HPV-18) 28 days after the last dose of Cervarix.

The individual tested hypotheses for the antigen “i” will be as follows:

$$H_0^i: P_{Group1}^i - P_{Group2}^i \leq -\delta$$

$$H_1^i: P_{Group1}^i - P_{Group2}^i > -\delta$$

where the non-inferiority limit  $\delta$  is set at 5% for each antigen “i”.

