##### ***Descriptive analysis on Cervarix and CYD dengue vaccine immunogenicity***

No hypotheses will be tested.

Immunogenicity point estimates and their 95% CI will be presented for each and any group, at baseline and after each dose of Cervarix and CYD dengue vaccine.

A complementary analysis on CYD dengue vaccine immunogenicity after each dose will be conducted for each and any group according to the dengue status at baseline (dengue immune, dengue non-immune, and all subjects).

The 95% CIs will be calculated using:

- The normal approximate method for GMs and GMTRs  
Assuming that  $\text{Log}_{10}$  transformation of the titers / data follows a normal distribution, at first, the mean and the 95% CI will be calculated on  $\text{Log}_{10}$  (titers / data) using the usual calculation for normal distribution (using Student’s t distribution with  $n-1$  degree of freedom), then antilog transformations will be applied to the results of calculations, in order to provide geometric means (GMs) and their 95% CI.
- The exact binomial distribution for single proportions (Clopper-Pearson’s method, quoted by Newcombe)

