### **5.5 Determination of Sample Size and Power Calculation**

A total of 480 subjects will be enrolled: 240 subjects in each group.

The reference standard deviations (SD) considered for Cervarix are 0.4 for both HPV-16 and HPV-18.

The reference seroconversion rates for Cervarix were set to 99% for both antigens.

The reference SD considered are the following for CYD dengue vaccine: 0.9 for serotype 1, 0.7 for serotypes 2 and 3 and 0.5 for serotype 4 (based on CYD13 and CYD15 efficacy studies conducted in subjects aged 9 to 16 years in Latin American countries).

Considering a potential attrition rate of 15%, such sample size would provide 204 evaluable subjects in the per protocol (PP) population per group. This will give, for the co-primary objectives, a global power of 90.2% and for secondary objectives (in terms of Cervarix seroconversion) a power of 91.8%.

Following Protocol Amendment 1, the number of evaluable subjects may be difficult to achieve (considering only dengue immune (seropositive) subjects at baseline to be included in the Per-Protocol populations). Thus the non-inferiority testing will be done only if the number of evaluable subjects provides a global power of at least 80% for the co-primary objectives and secondary objective ie, if the number of evaluable subjects is at least 163 per group for the co-primary objectives and 168 per group for the secondary objective. The power for non-inferiority in terms of GMTs per antigen and serotype is detailed in Table 5.1 and Table 5.3.

This initial study sample size will also provide a 95% probability of observing an AE that has a true incidence of 1.2% in each group (regardless of baseline serostatus).

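### If the 80% power gate is missed, no between-group GMT ratio or seroconversion difference with a confidence interval is planned

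*SAP*

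**What the plan says.** SAP 5.1 (same rule in Protocol 12.1) makes the non-inferiority tests conditional on at least 80% global power. SAP 5.5 turns this into evaluable numbers: 163 per group for the co-primary GMTs and 168 per group for Cervarix seroconversion. If the condition fails, "In case the global power is insufficient to perform non-inferiority testing, only descriptive analyses will be performed".

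Two between-group intervals are planned, and both are introduced as the way a gated test is carried out:

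- SAP 5.1.1.2, for GMTs: "The non-inferiority test will be performed using the 95% 2-sided CI of the difference of the means of the" log10 titers in the two groups.
- SAP 5.1.2.2, for seroconversion: the Wilson-score (Newcombe) interval for the difference in rates.

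The descriptive immunogenicity analysis in SAP 5.1.2.2 reads: "Immunogenicity point estimates and their 95% CI will be presented for each and any group, at baseline and after each dose". SAP Table 5.1 lists what this means for titers: log10 mean and SD, geometric mean with its interval, quartiles, range and reverse cumulative curves. For categorical results it gives numbers and percentages with intervals. All of these are single-group statistics.

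A titer ratio (GMTR) also appears. Its separate rules for values below LLOQ in the numerator and the denominator (SAP 4.4.2.1) fit a within-subject ratio, not Group 1 over Group 2.

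SAP 5.2.5 assigns PPX and PPC to the non-inferiority tests and sends all other immunogenicity analyses to the FAS by baseline dengue status.

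**The concern.** Protocol 1.4 gives the main purpose as showing that the two vaccines can be given together safely and without harming either immune response. The second part is a comparison between randomised groups. The plan estimates that comparison only inside the gated tests, so missing the gate removes the estimate along with the test. It also leaves the per-protocol sets with no assigned immunogenicity analysis.

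The gate applies to the product of six powers, and dengue serotype 1 (the largest SD) drives it. Too few subjects for serotype 1 would therefore also switch off the Cervarix GMT comparison, which needs far fewer.

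The sponsor treats a shortfall as possible: SAP 5.5 says the evaluable number may be hard to reach once only dengue-immune subjects count. The report would then show separate GMTs and intervals for each group, with no stated estimate of interference between the vaccines.

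**Working it through.** **Inputs (SAP 5.1.1.1, 5.1.2.1, 5.5)**

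- GMT margin: "non-inferiority limit is set at 2, ie, 0.301" on the log10 scale.
- HPV SDs: "The reference standard deviations (SD) considered for Cervarix are 0.4 for both HPV-16 and HPV-18".
- Dengue SDs: "0.9 for serotype 1, 0.7 for serotypes 2 and 3 and 0.5 for serotype 4".
- Seroconversion: "The reference seroconversion rates for Cervarix were set to 99% for both antigens"; the margin "is set at 5% for each antigen".
- One-sided alpha 2.5% per endpoint; all six GMT endpoints must pass.
- Assumed, because the documents do not state it: true GMT ratio 1 and endpoints independent.

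**Step 1. Reproduce the gate.** For n per group, SE = SD × √(2/n) and the non-centrality is 0.301/SE. Power is the chance that a non-central t with 2n − 2 df exceeds its 97.5% critical value. At n = 163:

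| Endpoint | SE | 0.301/SE | Power | Plan |
|---|---|---|---|---|
| HPV-16, HPV-18 | 0.0443 | 6.79 | >99.9% | >99.9% |
| Serotype 1 | 0.0997 | 3.02 | 85.3% | 85.3% |
| Serotypes 2, 3 | 0.0775 | 3.88 | 97.2% | 97.2% |
| Serotype 4 | 0.0554 | 5.44 | >99.9% | >99.9% |

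The product is about 0.853 × 0.972² = 0.806, against the stated 80.3%. At n = 204 it is 0.921 × 0.991² = 0.904, against 90.2%. For seroconversion, the Farrington-Manning formula gives 95.8% per antigen and 91.8% jointly at 204, and 89.6% and 80.4% at 168, all as stated. The gate figures are sound.

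**Step 2. Does low n invalidate the interval?** The rule compares a 95% confidence limit with a fixed margin.

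- A t-based interval on normally distributed log10 titers has a one-sided error of 2.5% at any n.
- With a normal quantile the error is 2.87% at n = 20, 2.57% at 100 and 2.54% at 160 per group.
- The Newcombe interval, enumerated exactly at true rates of 94% and 99% (the margin), gives 0.5% at n = 40, 1.5% at 100 and 1.9% at 160, so it is conservative.

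The gate depends on n and not on the results, so reporting the interval below it spends no alpha.

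**Step 3. How informative is the interval below the gate?** Take n = 102 per group as an example (half of 204; an assumption). The half-width is 1.972 × SD × √(2/102) = 1.972 × SD × 0.1400, and 10 to that power is the factor around the estimated ratio.

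| Endpoint | Half-width (log10) | Factor | Power |
|---|---|---|---|
| HPV-16, HPV-18 | 0.110 | ×/÷1.29 | 99.96% each |
| Serotype 1 | 0.248 | ×/÷1.77 | 66.2% |
| Serotypes 2, 3 | 0.193 | ×/÷1.56 | 86.4% |
| Serotype 4 | 0.138 | ×/÷1.37 | 99.0% |

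Every factor is below the two-fold margin. Joint HPV power is 0.9996² = 99.9%. All six together: 0.999 × 0.662 × 0.864² × 0.990 = 49%. If the four serotypes correlate at 0.5 (assumed), the figure is about 58%.

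**Step 4. Range.** If 50, 60, 70 or 75% of the 204 were evaluable (assumed), n is 102, 122, 142 or 153 per group. Power for all six is then 49, 62, 72 or 77%. The two HPV antigens alone reach 80% joint power at 38 per group.

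**The case against.** The best defence is that the gate is pre-specified, turns on sample size and not on outcome, inflates no error and biases no planned estimate. Declining a confirmatory claim from an underpowered comparison is conservative and openly stated. All of that stands, and it is why the point concerns the content of the fallback and not the gate.

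Several stronger readings are tempting, and the documents do not support them.

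- **The trial's only question goes unanswered.** Safety and descriptive immunogenicity are secondary objectives (SAP 2.2) and proceed regardless. Non-inferiority is the main question and the only one tested.
- **The plan forbids a between-group ratio.** It does not. The gap rests on silence. A reader with group sizes could rebuild a GMT ratio and interval from the log10 means and SDs in SAP Table 5.1, but on the FAS immune stratum and not on PPX or PPC.
- **About 80% of girls must be dengue-immune and accept dose 3.** The ratio 163/204 = 80% uses a denominator already cut by 15% attrition. Against the 240 enrolled per group it is 163/240 = 68%. PPX does not require dose 3, since its vaccination criteria end at V05/V06.
- **The power rule and the number rule conflict when arms are unequal.** SAP 5.5 gives the working rule as a number per group under 1:1 allocation. An imbalance large enough to separate the two is a corner case.
- **The gate should become a planning statement only.** It conditions the objectives themselves (Protocol 2.1 and 2.2). Removing it would change a protocol rule and involves a trade-off that this point does not need.

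**Conclusion.** The point holds as an omission in the fallback, and it should be fixed. Below the gate, the comparison that the trial was randomised to make has no planned estimate or interval, although one would be valid and often informative. At an assumed 102 per group, the Cervarix GMT ratios would be known to within about ×/÷1.29. The widest dengue interval would be about ×/÷1.77, inside a two-fold margin if the estimated ratio is near 1.

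These sizes rest on the plan's SDs. The powers also assume a true ratio of 1 and independent endpoints. Validity at any n is exact for a t-based interval under log-normality and close to exact for a normal-quantile interval except at very small n. The documents give neither the dengue-immune proportion nor the final evaluable numbers, so a reader should not infer that the gate was missed. The plan's power figures are not in error.

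**What to change.** In SAP 5.1, 5.1.1.2 and 5.1.2.2, state that the following are reported whatever the evaluable number and shown against their margins, each with a 2-sided 95% interval:

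- Group 1/Group 2 GMT ratios for HPV-16 and HPV-18 on PPX.
- Group 1/Group 2 GMT ratios for the four dengue serotypes on PPC.
- Group 1 minus Group 2 seroconversion differences for both HPV antigens on PPX.

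Below the gate, label them descriptive and low-powered and make no confirmatory non-inferiority claim. An interval that crosses the margin is then reported as inconclusive. Extend SAP 5.2.5 so that PPX and PPC serve these estimates as well as the tests, and list the addition in SAP 5.7. The gate itself stays as written in the protocol.

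The cost is SAP wording and a few output tables, with no extra data. The one downside is that a possibly inconclusive interval has to be worded with care.

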### 5.1.1 Hypotheses and Statistical Methods for Primary Objectives

#### 5.1.1.1 Hypotheses

##### ***Non-inferiority on Cervarix***

The objective is to demonstrate that the humoral immune response to Cervarix administered concomitantly with CYD dengue vaccine is non-inferior to the immune response to Cervarix administered sequentially with CYD dengue vaccine.

Individual hypotheses on Cervarix response for each antigen:

A non-inferiority testing approach will be used to compare geometric mean of titer (GMTs) for the 2 antigens (HPV-16 and HPV-18) 28 days after the last dose of Cervarix, based on the following individual hypotheses:

$$H_0^i: \text{GMT}_{\text{Group1}}^i / \text{GMT}_{\text{Group2}}^i \leq \frac{1}{\delta} \Leftrightarrow \log_{10}(\text{GMT}_{\text{Group1}}^i) - \log_{10}(\text{GMT}_{\text{Group2}}^i) \leq -\log_{10}(\delta)$$

$$H_1^i: \frac{1}{\delta} < \text{GMT}_{\text{Group1}}^i / \text{GMT}_{\text{Group2}}^i > \frac{1}{\delta} \Leftrightarrow \log_{10}(\text{GMT}_{\text{Group1}}^i) - \log_{10}(\text{GMT}_{\text{Group2}}^i) > -\log_{10}(\delta)$$

with:

i, antigen (HPV-16 and HPV-18)

$\delta$  non-inferiority limit is set at 2, ie, 0.301 ( $=\log_{10}[2]$ ), for each antigen "i"

Non-inferiority for antigen i will be demonstrated if the lower bound of the 2-sided 95% CI is greater than  $-\delta$  ( $\alpha=2.5\%$  one-sided).

##### Global hypotheses for non-inferiority on Cervarix response

The global hypotheses are:

$H_0^G$ : Non inferiority of Cervarix co-administered with CYD dengue vaccine versus Cervarix administered sequentially with CYD dengue vaccine is not demonstrated for at least one antigen.

$H_1^G$ : Non-inferiority of Cervarix co-administered with CYD dengue vaccine versus Cervarix administered sequentially with CYD dengue vaccine is demonstrated for all the antigens.

$H_0^G$  : at least one  $H_0^i$  not rejected

$H_1^G$  : all  $H_0^i$  are rejected

### ***Non-inferiority on CYD Dengue Vaccine***

The objective is to demonstrate that the humoral immune response to the CYD dengue vaccine administered concomitantly with Cervarix is non-inferior to the immune response to CYD dengue vaccine administered sequentially with Cervarix.

Individual hypotheses on CYD response for each antigen:

A non-inferiority testing approach will be used to compare GMTs 28 days after the third injection of CYD dengue vaccine between groups for each serotype “i” based on the following individual hypotheses:

$$H_0^i: \text{GMT}_{\text{Group1}}^i / \text{GMT}_{\text{Group2}}^i \leq \frac{1}{\delta} \Leftrightarrow \log_{10}(\text{GMT}_{\text{Group1}}^i) - \log_{10}(\text{GMT}_{\text{Group2}}^i) \leq -\log_{10}(\delta)$$

$$H_1^i: \frac{1}{\delta} < \text{GMT}_{\text{Group1}}^i / \text{GMT}_{\text{Group2}}^i > \frac{1}{\delta} \Leftrightarrow \log_{10}(\text{GMT}_{\text{Group1}}^i) - \log_{10}(\text{GMT}_{\text{Group2}}^i) > -\log_{10}(\delta)$$

with:

i, serotypes in {1, 2, 3, 4}

$\delta$  non-inferiority limit is set at 2 ie, 0.301 ( $=\log_{10}[2]$ ), for each serotype “i”

Non-inferiority for serotype i will be demonstrated if the lower bound of the 2-sided 95% CI is greater than  $-\delta$ .

Global hypotheses for non-inferiority on CYD response

$H_0^G: \text{at least one } H_0^i \text{ not rejected}$

$H_1^G: \text{all } H_0^i \text{ are rejected}$

Overall, non-inferiority among the groups will be demonstrated if, for each antigen of Cervarix and each serotype of CYD dengue vaccine, the 2-sided 95% CIs lie above  $-\delta$ .

#### **5.1.1.2 Statistical Methods**

The non-inferiority test will be performed using the 95% 2-sided CI of the difference of the means of the  $\log_{10}$  transformed post- vaccination titers between Group 1 and Group 2 ( $\alpha=2.5\%$  one-sided). The CI for differences will be calculated using normal approximation of log-transformed titers.

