## 3 Description of the Overall Trial Design and Plan

### 3.1 Trial Design

This is a Phase IIIb, randomized, open-label, multicenter study in 480 healthy female subjects aged 9 to 14 years in Mexico.

Subjects were to be randomized in a 1:1 ratio into one of the 2 following groups to receive:

- Group 1 (N=240): 3 doses of CYD dengue vaccine and 2 doses of Cervarix (Human Papillomavirus Bivalent [Types 16 and 18] Vaccine, Recombinant; GlaxoSmithKline) concomitantly to the 2 first doses of CYD dengue vaccine
- Group 2 (N=240): 3 doses of CYD dengue vaccine and 2 doses of Cervarix sequentially to the 2 first doses of CYD dengue vaccine

For both vaccines, each dose is to be administered 6 months apart.

As per Protocol Amendment 1, only subjects identified as dengue immune (seropositive) before administration of the first CYD dengue injection (at V01 for Group 1 and at V02 for Group 2) and who consented to receive the remaining injection of dengue vaccine could remain in the study as per initial study procedures.

Subjects identified as non-immune (seronegative) at baseline could continue in the study for a 6-month safety follow-up. They did not receive the third and last injection of the CYD dengue vaccine.

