#### 4.4.5 Baseline Dengue status

The dengue serostatus at baseline is defined as the presence of Abs against at least one dengue serotype in the baseline sample (by dengue 50% plaque reduction neutralization test [PRNT50]) in the blood sample collected at V01 for group 1 and at V02 for group 2. The baseline dengue status will be derived for each subject as follows:

- Dengue immune subjects (seropositive) at baseline are defined as those subjects with titers  $\geq 10$  (1/DIL) for at least one serotype with the parental dengue virus strain.
- Dengue non-immune subjects (seronegative) at baseline are defined as those subjects with titers  $< 10$  (1/DIL) (not quantified) for all serotypes with parental dengue virus strains with available and “valid” results (i.e. not coded “NR”) in the serology database.
- Otherwise the baseline status will be classified as undetermined and subjects will have their dengue baseline status derived as non-immune.

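### The CYD non-inferiority interval is valid but leaves out the pre-CYD dengue titre already measured, so it is wider than it needs to be

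*SAP*

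**What the plan says.** SAP 5.1.1.2 and Protocol 12.1.1.2 compare the groups on the difference in mean log10 post-vaccination titre and add: "The CI for differences will be calculated using normal approximation of log-transformed titers". For CYD the rule is: "Non-inferiority for serotype i will be demonstrated if the lower bound of the 2-sided 95% CI is greater than" minus delta, where the "non-inferiority limit is set at 2 ie, 0.301" on the log10 scale. All four serotypes must pass.

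Neither document has a covariate-adjusted analysis, main or supportive. The baseline dengue titre is used to set serostatus and in descriptive summaries only.

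The titre is nevertheless collected. SAP 4.4.5 takes baseline status from PRNT50 "in the blood sample collected at V01 for group 1 and at V02 for group 2", and Protocol 9.1.1.2 reports titres as continuous values with an LLOQ of 10. The CYD per-protocol set (PPC, SAP 5.2.2) excludes seronegative girls, and SAP 4.4.5 derives undetermined status as non-immune.

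SAP 5.5 gives log10 SDs of "0.9 for serotype 1, 0.7 for serotypes 2 and 3 and 0.5 for serotype 4". It runs the co-primary tests only with at least 163 evaluable girls per group. Otherwise SAP 5.1 makes the analysis descriptive.

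**The concern.** Since Amendment 1 the CYD test is run only in dengue-immune girls. Immune status needs a titre of 10 or more for just one serotype, so a given serotype's pre-CYD titre can lie anywhere from below 10 upwards. Protocol 1.4 notes that PRNT cannot separate antibody to wild-type dengue from antibody to the vaccine virus. Whatever a girl carried in is therefore part of what the post-dose-3 assay reads, which makes a positive correlation plausible.

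Leaving out a prognostic baseline value does not bias a randomised comparison, but it leaves explainable variance in the interval. That matters here because all four serotypes must pass, serotype 1 with its SD of 0.9 limits global power, and the plan itself expects the evaluable number to be hard to reach.

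**Working it through.** **Inputs**
- One-sided alpha 0.025 and margin log10(2) = 0.301 (SAP 5.1.1.1).
- Dengue SDs 0.9, 0.7, 0.7 and 0.5; for HPV, the SDs "considered for Cervarix are 0.4 for both HPV-16 and HPV-18" (SAP 5.5).
- Allocation 1:1 (SAP 3.1); 240 x 0.85 = 204 evaluable per group planned, and the threshold of 163 (SAP 5.5).
- Assumed, because the documents do not state them: a true difference of 0, and r from 0 to 0.7.

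**Step 1: reproduce the plan's power.** For each endpoint, SE = SD x sqrt(2/n). Power is the probability that a non-central t with 2n - 2 degrees of freedom and non-centrality 0.301/SE exceeds its 97.5% critical value. Global power is the product over endpoints.

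Serotype 1 at n = 163: SE = 0.9 x sqrt(2/163) = 0.0997, non-centrality 3.02, power 85.3%. Serotypes 2 and 3 have 97.2% each, and serotype 4 and both HPV antigens exceed 99.9%.

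| n per group | Serotype 1, stated / recomputed | Serotypes 2 and 3, stated / recomputed | Global, stated / recomputed |
|---|---|---|---|
| 204 | 92.1% / 92.1% | 99.1% / 99.1% | 90.2% / 90.5% |
| 163 | 85.3% / 85.3% | 97.2% / 97.2% | 80.3% / 80.6% |

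The 0.3-point gap is rounding. Entering the three values above 99.9% as 0.999 gives 0.853 x 0.972² x 0.999³ = 0.803 and 0.921 x 0.991² x 0.999³ = 0.902. The plan's power thus rests on the full, unadjusted SDs.

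**Step 2: adjust for the pre-CYD titre.** With one baseline covariate the residual SD is SD x sqrt(1 - r²), so variance falls by r²: 9% at r = 0.3, 25% at 0.5 and 49% at 0.7. The HPV SDs are left alone. For serotype 1 at r = 0.5: residual SD = 0.9 x sqrt(0.75) = 0.779, SE = 0.779 x sqrt(2/163) = 0.0863, non-centrality 3.49, power 93.5%. The half-width below is 1.96 x SE.

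| r (assumed) | Serotype 1 residual SD | 95% CI half-width, serotype 1, n = 163 | Serotype 1 power, n = 163 | Global power, n = 163 | Global power, n = 204 |
|---|---|---|---|---|---|
| 0 | 0.900 | 0.195 | 85.3% | 80.6% | 90.5% |
| 0.1 | 0.895 | 0.194 | 85.7% | 81.1% | 90.8% |
| 0.2 | 0.882 | 0.191 | 86.7% | 82.7% | 91.8% |
| 0.3 | 0.859 | 0.186 | 88.4% | 85.3% | 93.3% |
| 0.5 | 0.779 | 0.169 | 93.5% | 92.4% | 97.1% |
| 0.7 | 0.643 | 0.140 | 98.8% | 98.7% | 99.7% |

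**Step 3: check the error rate.** In a simulation of serotype 1 at 163 per group (10,000 runs per setting, r = 0, 0.3, 0.5 and 0.7), ANCOVA rejected at the margin in 2.3% to 2.8% of runs and the unadjusted test in 2.3% to 2.9%. At r = 0, power was 85.2% adjusted and 85.4% unadjusted, so adjustment costs almost nothing if the baseline proves uninformative.

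**The case against.** **The threshold.** A reader might infer that adjustment would rescue the objective with fewer than 163 girls per group. The documents do not support that: 163 is a fixed count derived from unadjusted SDs, and below it no test is run, adjusted or not. Moving it would need a residual SD fixed in advance, and the documents offer no basis for one. This objection stands, and it confines the gain to 163 per group and above.

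**The size.** The value of r is unknown. The reference SDs carry no stated serostatus restriction, while the test is now confined to immune girls; that restriction may lower both the SD and r. At r of 0.1 to 0.2 the gain is small. This stands too.

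**Availability.** A reader might infer that every per-protocol girl has a baseline titre for all four serotypes. PPC guarantees a valid result for at least one only.

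**The post-randomisation baseline.** Group 2's sample follows Cervarix dose 1, so adjustment assumes that Cervarix does not change dengue titres. The documents do not test this. But the sample precedes any CYD dose, Cervarix's listed contents (Protocol 6.1.2.1) are HPV proteins, adjuvant and excipients, and the same sample already decides PPC membership. The retained unadjusted interval is a check.

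**Adequacy and lateness.** At 163 or more the plan already meets its own 80% target, and changing a primary estimator late in an open-label trial has a credibility cost. The first does not make cheap precision worthless when four serotypes must all pass. The second is why the change must come before any by-group analysis.

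**Conclusion.** The point holds as a loss of efficiency. It would be wrong to read it as a finding of bias, an inflated error rate or an invalid interval: the planned comparison matches its stated hypothesis and has the right error rate.

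At 163 per group, using the pre-CYD titre would raise global power from 80.6% by 0.5 points at r = 0.1, 2.1 at r = 0.2, 4.7 at r = 0.3, 11.8 at r = 0.5 and 18.1 at r = 0.7. Which of these applies cannot be settled from the documents. The figures assume a true difference of zero, the plan's SDs, a linear relation with the same r for every serotype, and the product rule that reproduces the plan's own global power. The change is worth making because it costs so little even when r is low.

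**What to change.** Before any by-group analysis, amend SAP 5.1.1.2 so that, for each serotype, the main CYD comparison is an ANCOVA of log10 post-dose-3 titre on group and that serotype's log10 pre-CYD titre, with values below LLOQ set to half the LLOQ as the plan already does for GMTs. Test the lower bound of the two-sided 95% CI for the adjusted Group 1 minus Group 2 difference against -0.301. Keep the unadjusted interval as a sensitivity analysis, and leave the 163 threshold as it is.

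Align Protocol 12.1.1.2 and the synopsis. Reconcile the baseline definition as well: Protocol 9.1.1.1 places the serostatus sample at V01 for all girls, whereas Protocol 9.1.1.2, the schedule and SAP 4.4.5 place Group 2's pre-CYD dengue sample at V02. Protocol 9.1.1.1 and SAP 4.4.5 also treat missing baseline titres differently.

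HPV needs no change: its power exceeds 99.9%, and the Cervarix per-protocol set excludes girls seropositive for HPV at baseline.

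The cost is wording in both documents and four models. A girl with a missing or non-reportable baseline titre for one serotype drops from that serotype's adjusted model, and the number lost should be reported. State openly that Group 2's covariate is measured after randomisation and Cervarix dose 1.
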